Statistical Analysis Plan (SOP)

Parent study Title: “The Effect of Plasma Donation Frequency on Plasma Protein Composition, Inflammation Markers and Psychological Distress - a Randomized Controlled Trial”

Sub Study Title: “The Effect of Plasma Donation Frequency on PFAS Concentrations – a randomized controlled trial”

ClinicalTrials.gov Reference: NCT05179200

Date: 01.09.2025

Introduction

Background and Rationale

Poly- and perfluoroalkyl substances (PFAS) are synthetic compounds used for their water- and fat-repellent properties in products such as textiles, food packaging, cosmetics, and electronics [1-3]. PFAS are highly persistent in the environment and the human body, with long biological half-lives of 1-5 years [4]. As a result, they are widely detected in drinking water, soil, and food. Exposure in humans primarily occurs through the ingestion of contaminated water and food, as well as through everyday consumer products such as non-stick cookware, water-repellent clothing, food packaging, dental floss, and cosmetics. PFAS are absorbed into the bloodstream and bind to proteins rather than fat [3, 5-7], leading to bioaccumulation over time [1, 8]. This accumulation has been linked to adverse health effects, including immune suppression, hormonal disruption, elevated cholesterol, and potential carcinogenicity [9].

PFAS exposure is primarily assessed through blood concentrations. A recent Swedish study investigated PFAS exposure in the general population and analysed samples from 60 blood donors [10]. They detected 26 of 30 different PFAS and observed PFHxS-lin, PFOS (linear and branched), PFOA-lin, PFNA, and PFDA in all samples, and found the highest concentrations of PFOS-lin, PFOS-br, PFOA-lin, and PFHxS-lin.

A previous RCT in Australian firefighters, with high exposure to PFAS through firefighting foams, demonstrated reductions in PFAS concentrations following plasma donations every 6 weeks and blood donations every 12 weeks [11].

In this study, we aim to investigate the effect of different plasma donation frequencies on PFAS concentrations in blood donors.

Objectives

To compare the plasma concentration of different PFAS at baseline and after 16 weeks of donations between high-frequency plasma donors (HFPDs), donating plasma 3 times every 2 weeks, regular-frequency plasma donors (RFPDs), donating plasma once every 2 weeks, and a control group (controls) donating whole blood every 3 months.

Study Methods

Trial Design

This is a randomized controlled trial, parallel-group, where 120 male blood donors were randomized 1:1:1 for donation over 16 weeks to:

- High-frequency plasma donors (HFPDs) donating plasma 3 times every 2 weeks (in total 24 times)
- Regular-frequency plasma donors (RFPDs) donating plasma once every 2 weeks (in total 8 times)
- The control group (controls) donating whole blood every 3 months (in total 2 times)

The study was conducted at the Blood Centre of Innlandet Hospital Trust from January 2022 to July 2024.

Trial Population

Established male blood- and plasma donors aged between 18 and 64 years were screened for eligibility. The inclusion criteria were sufficient levels of Hb, TSP, and IgG, an estimated blood volume (EBV) of at least 4500 mL, a donation history of at least one previous plasma donation, and the donors had to meet the eligibility criteria for both whole blood and plasma donation by plasmapheresis. Donors with a history of repeated measurements (>2) of haematocrit >50 % before enrolment were excluded.

All participants provided written informed consent. The study was approved by the Regional Committee for Medical and Health Research Ethics in Southeast Norway (2021/238929/REC Southeast A) and was conducted in accordance with the Declaration of Helsinki. The study is registered at clinicaltrials.gov (identifier: NCT05179200).

Intervention

The plasmapheresis procedure was performed using the Aurora Plasmapheresis machine, Fresenius Kabi. The plasma donation volume was 720 mL, including AC, which corresponds to approximately 650 mL plasma, excluding AC, assuming a haematocrit of 44% and an ACR of 100:6. The whole blood donations were 450 mL of whole blood.

Data Collection

Baseline data were collected through questionnaires and from the blood centre's database, LabCraft.

Blood Samples and Analyses

One tube of 6 mL EDTA plasma was collected non-fasting per participant immediately before the plasmapheresis procedure, at:

- Baseline week 1 (W1): Before the first donation in the study, after at least two months of no donation.
- End point week 18 (W18): Two weeks after the final donation.

The plasma samples were centrifuged at 2200×g for 10 min immediately after collection, transferred into aliquots of 500 µL, and frozen at -40°C within 3 hours after collection. Within 3 months of storage, the samples were transferred to storage at -80°C until analysis. The samples were shipped on dry ice to the laboratory for analysis. PFAS analyses were conducted at the Environmental Pollutant Laboratory, University Hospital of North Norway, Tromsø, Norway, according to the method described by Huber and Brox [12]. Samples were analysed in two batches of 96 samples in 2023 and 122 samples in 2024.

Variables

Outcome Measures

Difference in plasma concentrations between W1 and W18 of the following PFAS:

Primary outcomes:

- Perfluorooctanoic acid (PFOA)
- Perfluorooctane sulfonic acid (PFOS)*
- Perfluorohexane sulfonic acid (PFHxS)*
- Perfluorononanoic acid (PFNA)
- Sum of PFOA, PFOS, PFHxS and PFNA [13]

Secondary outcomes:

- Perfluorobutanoic acid (PFBA)
- Perfluoropentanoic acid (PFPeA)
- Perfluorohexanoic acid (PFHxA)
- Perfluoroheptanoic acid (PFHpA)
- Perfluorodecanoic acid (PFDA)
- Perfluoroundecanoic acid (PFUDA)
- Perfluorododecanoic acid (PFDaDA)
- Perfluorotridecanoic Acid (PFTrDA)
- Perfluorotetradecanoic acid (PFTeDA)
- Perfluorobutane sulfonic acid (PFBS)
- Perfluoropentane sulfonic acid (PFPS)
- Perfluorooctane sulfonic acid (PFHpS)*
- Perfluorononane sulfonic acid (PFNS)*
- Perfluorodecane sulfonic acid (PFDS)*
- Perfluorodecane sulfonic acid (PFDaDS)
- Perfluorooctane sulfonamide (PFOSA)*
- 4:2 Fluorotelomer sulfonic acid (4:2 FTSA)
- 6:2 Fluorotelomer sulfonic acid (6:2 FTSA)
- 8:2 Fluorotelomer sulfonic acid (8:2 FTSA)
- 10:2 Fluorotelomer sulfonic acid (10:2 FTSA)

*Analysed as linear and branched isomers, and the sum of these.

Other variables:

- Plasma albumin concentration (as a mediator)

Independent Variables

- Study group identity (HFPDs, RFPDs, control group)

Statistical Analysis

Stata (StataCorp, College Station, TX, USA) will be used for the statistical analyses.

Outcome variables will be checked for normality. Normally distributed data will be expressed as mean (SD), and non-normally distributed data will be expressed as median (min-max and/or IQR). 95% confidence intervals will be used, and a two-tailed p-value < 0.05 will be considered statistically significant.

Samples below the detection and quantification limits:

- The number, n (%), of samples below the limit of quantification (LOQ), as defined per the laboratory protocol, will be calculated.
- The number, n (%), of samples below the limit of detection (LOD) will be calculated.
- Only PFAS (or summarized variables) with a detection rate >70% at baseline will be included in the statistical analysis [14, 15].

For values below the LOD, a common imputation approach will be used where concentrations are replaced by LOD/2 (i.e., one-half the detection limit). Sensitivity analyses may be conducted to evaluate the choice of imputation method for values below the LOD (e.g., LOD/2, LOD/ $\sqrt{2}$, or exclusion of values below the LOD) to assess the robustness of the imputation strategies.

Branched isomers of PFHxS, PFHpS, PFOS, PFNS, PFDS, and PFOSA will be calculated as:
Branched = sum – linear.

The difference in PFAS concentrations within each group from baseline at W1 to the end point at W18 between the study groups will be estimated using generalized linear models (or similar methods). For continuous outcomes, we will use an identity link function and assume a Gaussian distribution family.

We will also consider analyses using other distribution families based on the skewness of the data, as well as whether to categorize (e.g., dichotomize) the outcome variable.

We will also consider quantile regression and express the effects as the median differences between the study groups.

Bootstrap confidence intervals (95%) for median concentrations and median changes will be calculated using 1,000 resampling iterations to provide robust estimates that are not sensitive to non-normality.

We will also use mediation analyses to estimate the extent to which the effect is mediated through changes in albumin concentration.

Results

Figures

Flow chart of participants and samples, including ITT and PP populations and the number of donations.

Plots showing the concentration of different PFAS from week 1 to week 18.

Tables

Table 1: Baseline characteristics

	HFPDs	RFPDs	Control group
Age			
Height			
Weight			
BMI			
Donation history			
• Plasma			
• Whole blood			
Occupation			

Table 2: Baseline concentration of PFAS (incl. branched and linear isomers)

	HFPDs	RFPDs	Control group
PFBA (ng/mL)			
...			

Table 3: Concentrations of PFAS at W18 and change from W1

PFAS	HFPDs		RFPDs		Control group	
	W18	W18-W1	W18	W18-W1	W18	W18-W1
PFBA (ng/mL)						
...						

*p-value compared to controls at W18

Ethical considerations and data storage

All data and analyses are securely stored and managed on a safe dedicated server at Innlandet Hospital Trust. This study was funded by Innlandet Hospital Trust, Norway.

Supplementary

Table S1: Individual limits of detection (LOD) of PFAS:

PFAS	Range	Median	Mean
PFBA (ng/mL)			
...			

Table S2: Detection frequencies of analysed PFAS in all samples and per intervention group.

PFASs	All samples	All samples W1	All samples W18	HFPD		RFPD		Control	
				W1	W18	W1	W18	W1	W18
PFBA (ng/mL)									
...									

Data are n (%)>LOD (n (%))>LOQ).

Authorship

Authorship for this paper will be determined based on the Vancouver Convention on authorship [16]:

[name] (MH, corresponding and first author)

[name] (KM)

[name] (SH)

[name] (LSHNM)

[name] (TAS)

The order of authorship may be revised according to the authors' respective contributions.

Timeline and Responsibilities

Task	Deadline	Responsibility
Completion and approval of SAP	August 2025	MH, SH, KM, TAS, LSHNM
Completion of data set	August 2025	MH, TAS
Drafting introduction and methods section	August 2025	MH, SH

Task	Deadline	Responsibility
Statistical analysis	September 2025	MH, TAS, LSHNM
Drafting results section	September/October 2025	MH, SH
Drafting discussion section	October 2025	MH, SH
Evaluation of paper draft	November/December 2025	MH, SH, KM, TAS, LSHNM,
Final manuscript submission	December 2025/January 2026	MH

References

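### Does running the PFAS assays in two batches, with no batch term in the change model, require a change to the analysis?

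*SAP*

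**What the plan says.** The Trial Design section says that "120 male blood donors were randomized 1:1:1 for donation over 16 weeks to" three arms, and that "The study was conducted at the Blood Centre of Innlandet Hospital Trust from January 2022 to July 2024". Each donor gives two samples. The first is defined as "Baseline week 1 (W1): Before the first donation in the study, after at least two months of no donation" and the second as "End point week 18 (W18): Two weeks after the final donation". On the assays, the SAP says only that "Samples were analysed in two batches of 96 samples in 2023 and 122 samples in 2024".

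The outcome is the difference in concentration between the two visits. The sole entry under Independent Variables is "Study group identity (HFPDs, RFPDs, control group"; albumin is listed separately, as a mediator. The Statistical Analysis section proposes generalized linear models or something similar: "For continuous outcomes, we will use an identity link function and assume a Gaussian distribution family". It names no batch term, and its one optional sensitivity analysis concerns values below the limit of detection. Results go into "Table 3: Concentrations of PFAS at W18 and change from W1", which has a within-group change column for each arm and p-values against controls.

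**The concern.** A 2023 assay run took place while donors were still in the study. If samples were sent as they accrued, donors who were between week 1 and week 18 at the cut-off would have their baseline in one batch and their endpoint in the other. A calibration difference between the runs would then look like a change in PFAS for those donors. Randomisation does not protect a within-group figure, so the change columns of Table 3 could show a rise or fall that is only assay drift, including in controls, where the reader looks to see whether anything happened. Choosing model terms is the SAP's own job, and this SAP mentions the batches without saying how they are handled.

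**Working it through.** The SAP gives no SD, effect size, drift or power, so there is no design figure to reproduce.

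**Inputs from the SAP.** 96 and 122 samples; 120 donors; visits at weeks 1 and 18 (17 weeks apart); study period January 2022 to July 2024.

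**Assumptions, not in the SAP.** Inter-batch drift of 5, 10 or 20%; within-person log SD 0.10 per sample; between-person log SD 0.5; no true change in controls; a true 5% fall for the power figures; all samples paired; batching by sampling date with uniform enrolment where pairs are split.

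**1. Do the counts show split pairs?** 96 + 122 = 218, which is 22 below 2 × 120 = 240. Three patterns fit:
- 48 intact pairs in 2023 and 61 in 2024 (2 × 48 = 96, 2 × 61 = 122);
- 40 pairs in 2023, 16 split and 53 in 2024 (2 × 40 + 16 = 96, 2 × 53 + 16 = 122);
- 120 baseline and 98 endpoint samples (120 + 98 = 218), that is 98 pairs and 22 single samples, divided between the batches in many possible ways.

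The counts do not tell these apart.

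**2. Plausible split share.** The study period is 126 to 134.6 weeks. Subtracting 17 leaves a week 1 window of 109 to 117.6 weeks. The share is 17/109 = 15.6% to 17/117.6 = 14.5%, about 16 of 109 pairs.

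**3. Within-group bias.** Split share × log(1 + drift), with 16/109 = 0.147:
- 5%: 0.147 × 0.0488 = 0.7%
- 10%: 0.147 × 0.0953 = 1.4%
- 20%: 0.147 × 0.1823 = 2.7%

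In simulation, a t-interval for the control arm's mean log change covers 94/92/84%, against 95% without drift. For the interval the plan does name, a bootstrap interval for the median change, the figures in ng/mL are about 94/92/88%, against about 94% without drift. These depend on the assumed SD: at 20% drift the log-scale interval covers about 65% if the SD is 0.05 and 89% if it is 0.15.

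**4. Between-group contrast, log change.** Variance ratio = 1 + p(1 − p) × log(1 + drift)² / (2 × 0.10²). At p = 0.15, p(1 − p) = 0.1275:
- 5%: 1 + 0.1275 × 0.00238/0.02 = 1.015
- 10%: 1 + 0.1275 × 0.00908/0.02 = 1.058
- 20%: 1 + 0.1275 × 0.0332/0.02 = 1.212

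Power for RFPDs against controls with a 5% fall goes from 33% to 33/32/28%. A batch-pattern factor brings the ratio to about 1.02 at every drift.

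**5. Between-group contrast, the plan's ng/mL scale.** Simulated variance ratios with 16 split pairs:

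| Drift | No batch factor | Batch-pattern factor |
|---|---|---|
| 5% | 1.05 to 1.07 | 1.08 |
| 10% | 1.17 to 1.19 | 1.15 to 1.17 |
| 20% | 1.47 to 1.49 | 1.31 to 1.32 |

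Most of the increase at 5 and 10% drift is not lost precision. With all pairs intact and 61 of 109 in 2024, the gross ratio is 48/109 + (61/109)(1 + drift)² = 1.06/1.12/1.25. The contrast itself is multiplied by 1 + drift × 61/109 = 1.028/1.056/1.112. Dividing the unrounded ratio by the squared multiplier gives 1.0006/1.002/1.008, a net loss below 1%.

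**The case for a change.** The best case for a change is that it is cheap and guards against a choice made after seeing the data. The split share in step 2 is not far-fetched, the within-group columns would carry the bias, and at 20% drift the control arm's interval would be clearly too optimistic. The freedom to use a similar method permits a batch term but does not promise one.

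Much of this stands as description: the SAP is silent on batch, and the within-group columns are the exposed part. It does not carry through to a change in the analysis. The harm needs split pairs and material drift together, and the SAP shows neither. How tubes were allocated to runs is a fact of laboratory conduct that need not be set out in a SAP. The comparison that answers the objective is between arms, and it stays unbiased as long as batching is unrelated to arm. The adjustment that works well does so on the log scale, where it would replace an absolute difference by a relative one. That is a different estimand and a separate choice. Restricting to same-batch pairs leaves 93 of 109 and raises the variance by about 109/93 = 1.17, which is too dear for a main analysis.

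**Conclusion.** The concern does not call for a change. If pairs were run together, the log change is unaffected, and the ng/mL contrast is only rescaled, by about 3/6/11% of its own size at 5/10/20% drift. If about 16 of 109 pairs were split, the within-group changes shift by 0.7/1.4/2.7% of level in the same direction in every arm. The between-group contrasts remain unbiased in expectation, and on the plan's scale a batch factor gains almost nothing at 5 or 10% drift. Only drift near 20% makes it worthwhile, and nothing in the SAP points to drift of that size. These sizes rest on the assumed drift, SD, pairing and date-based batching.

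This is missing detail that analysts can fill sensibly. The batch of each sample should be known from laboratory records, so a count by visit and arm settles whether any pair was split. If some were, a note beside the within-group columns and a sensitivity analysis on the plan's own scale fit within the latitude the SAP already gives.

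### The batch counts leave 11 to 22 of 120 randomised donors without a W1–W18 difference, and the difference model as described would drop them and not adjust for baseline

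*SAP*

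**What the plan says.** Under Trial Design the SAP states that "120 male blood donors were randomized 1:1:1 for donation over 16 weeks", to 24 plasma donations, 8 plasma donations or 2 whole-blood donations. Under Blood Samples and Analyses, one tube per participant is taken at each of two visits: "Baseline week 1 (W1): Before the first donation in the study, after at least two months of no donation" and "End point week 18 (W18): Two weeks after the final donation". The same section gives the assay counts: "Samples were analysed in two batches of 96 samples in 2023 and 122 samples in 2024".

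Under Outcome Measures, all outcomes, including the five primary ones, are defined as "Difference in plasma concentrations between W1 and W18 of the following PFAS". Independent Variables lists study group only. Statistical Analysis plans generalized linear models with identity link and Gaussian family, but leaves similar methods open. Its only imputation rule replaces values below the LOD with LOD/2; it has no rule for an absent W1 or W18 sample.

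Analysis populations appear once, under Results, Figures: "Flow chart of participants and samples, including ITT and PP populations and the number of donations". The SAP does not define them or say which one the model uses.

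**The concern.** The outcome needs two samples from the same donor, and the assay counts show that not every randomised donor supplied two. The SAP is dated 01.09.2025, after the study ended in July 2024 and after both assay batches, so the shortfall could be seen when the plan was written. It does not say what happens to the donors affected.

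Two things are at stake. First, the arms ask for 24, 8 and 2 donations, so losses after randomisation could differ by arm. If they also relate to response, a contrast based on complete pairs answers a narrower question than the effect of being assigned to a frequency. Second, a difference model with study group alone makes no use of how W18 depends on W1, so it gives up precision even when every pair is intact.

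**Working it through.** The SAP gives no total, number of pairs or power figure to reproduce, so the check is a count.

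**Inputs.** Donors randomised N = 120 (Trial Design). Samples per donor: 2, one at W1 and one at W18 (Blood Samples and Analyses). Samples assayed S = 96 + 122 = 218 (same section).

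**Shortfall.** Expected samples: 2 × 120 = 240. Missing: 240 − 218 = 22, or 22/240 = 9.2%.

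**Range of complete pairs**, if all 218 are unique participant samples:
- Maximum: S/2 = 218/2 = 109. Then 120 − 109 = 11 donors (9.2%) have neither sample assayed.
- Minimum: S − N = 218 − 120 = 98. Then 120 − 98 = 22 donors (18.3%) have one sample each.
- The range is the same if every donor with a W18 sample also has a W1 sample. The lower end then means that all 120 have W1 and 22 lack W18.

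**If some runs were repeats or controls.** With 10 such runs, S = 208, and pairs run from 208 − 120 = 88 to 208/2 = 104. So 11 donors without a pair is a floor.

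**Where in the range.** Both batch counts are even: 96/2 = 48, 122/2 = 61, and 48 + 61 = 109. That fits complete pairs only, but does not prove it.

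**Precision** (illustration: equal losses per arm, two arms compared, two-sided alpha 0.05). The standardised difference detectable with 80% power is (1.96 + 0.84) × √(2/n):

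| Pairs | n per arm | Detectable difference | Power where 40 per arm gives 80% |
|---|---|---|---|
| 120 | 40 | 0.63 | 80% |
| 109 | 36.3 | 0.66 | 76% |
| 98 | 32.7 | 0.69 | 72% |

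**What baseline adjustment gains with intact pairs.** Let ρ be the W1–W18 correlation within an arm and g the ratio of the W18 SD to the W1 SD. In units of the W1 variance, the change score has variance 1 + g² − 2ρg, and the baseline-adjusted W18 value has g²(1 − ρ²). The SAP gives neither ρ nor g, so these are assumed ranges:
- g = 1: the ratio is (1 + ρ)/2, so variance falls by 10%, 5% and 2.5% for ρ = 0.80, 0.90 and 0.95.
- g = 0.9, as after a proportional fall of about 10%: for ρ = 0.90, the change score has 1 + 0.81 − 1.62 = 0.19 and the adjusted value 0.81 × 0.19 = 0.154, a fall of 19%. For ρ = 0.80 and 0.95 it is 21%.

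The formula treats ρ and g as the same in each arm. If the fall differs by arm, the gain will differ too, but baseline adjustment is not expected to do worse than the change score on average.

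**The case against.** The other side is strong on what the SAP does not say. A reader might infer that it reports an ITT population of 120, or that it labels the difference analysis ITT. It does neither: ITT stands once, as flow-chart content, with no number and no link to the model. The protocol is not shown and may define the populations.

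A reader might also infer that the planned analysis is fixed as complete pairs. Dropping incomplete pairs is the default for a model of the difference, but the allowance for similar methods leaves a joint model open. Nor is every unpaired sample discarded: baseline samples enter the 70% detection rule and Table 2, Table 3 reports W18 concentrations apart from the change, and Table S2 counts samples by arm and visit.

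Putting a percentage on the bias is tempting too. Any such figure needs the losses by arm and the response of the lost donors, and the SAP gives neither. In the 11-donor case those donors have no assayed sample at all, so assuming that they completed part of the schedule has no basis in the document.

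Finally, the remedy has limits. A joint model cannot include donors with neither sample, and it assumes that missingness depends only on observed data. If all 218 samples are intact pairs, it brings in no further donors.

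All of this stands. It does not touch the count, the absence of a rule for absent samples, or the lack of baseline adjustment.

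**Conclusion.** The point holds in this limited form. If the 218 assays are unique participant samples, 98 to 109 of 120 donors have a W1–W18 difference and 11 to 22 (9–18%) do not; if some runs were repeats or controls, more donors are affected. The split by arm is unknown. The model as described would drop these donors by default and would not adjust for baseline, and no population is tied to it.

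The direction and size of any resulting bias cannot be worked out from the SAP, and the bias is zero if the loss is unrelated to response. The loss of precision is moderate: power falls from 80% to about 76% or 72% with equal losses per arm. Baseline adjustment could win some of it back, by an amount that depends on ρ and g. This should be changed before analysis, but it does not by itself invalidate the trial.

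**What to change.** In Statistical Analysis:

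1. Make the primary model a joint linear model of W1 and W18 for each outcome, with a common mean at W1 across arms, arm-specific means at W18 and an unstructured covariance for the two visits. Analyse donors in their assigned arm. The contrast of interest is the difference between arms at W18. Every assayed sample is then used and the contrast is baseline-adjusted.
2. State which named population this model uses. Describe any change-score result as complete pairs, and give the number of pairs by arm. The flow chart and Table S2 come close to this already, but Table S2 counts samples, not pairs.
3. Optionally, add one sensitivity analysis for donors without a W18 value, for example giving those in the plasma arms the control-arm change. If a fraction f of a plasma arm is treated this way, its mean change relative to control is multiplied by 1 − f. With losses spread evenly, f runs from 11/120 to 22/120, so the contrast shrinks by 9% to 18%. This shows robustness; it does not estimate bias.

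The cost is a few sentences, one extra model per outcome in Stata and possibly one sensitivity analysis, with no new data. The downside is a normality assumption at both visits, which matters because the SAP itself foresees skewed concentrations.

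### The change model lists study group only; adding the measured W1 level would modestly sharpen the HFPD contrasts on the raw scale (a precision point, not a bias)

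*SAP*

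**What the plan says.** Under Variables, Outcome Measures, the SAP defines the outcomes as "Difference in plasma concentrations between W1 and W18 of the following PFAS". Under Independent Variables the only entry is "Study group identity (HFPDs, RFPDs, control group"). Albumin is listed apart from this, as a mediator.

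Under Statistical Analysis, the change "from baseline at W1 to the end point at W18 between the study groups will be estimated using generalized linear models", with similar methods allowed. The SAP continues: "For continuous outcomes, we will use an identity link function and assume a Gaussian distribution family". Other distribution families, categorisation and quantile regression are to be considered, and bootstrap intervals are planned for medians. W1 enters the change score, the baseline table and the detection-rate rule, but no sentence makes it a covariate.

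The Objectives cover all three groups: "To compare the plasma concentration of different PFAS at baseline and after 16 weeks of donations between high-frequency plasma donors (HFPDs"), the RFPDs and the controls. HFPD-RFPD is therefore a stated comparison, alongside the two contrasts with controls.

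**The concern.** W1 is drawn before the first study donation, so it is a valid baseline covariate, and it is likely to predict raw change. The Intervention section says "The plasma donation volume was 720 mL, including AC, which corresponds to approximately 650 mL plasma". The mass of PFAS removed by a fixed volume scales with the donor's own level. The Trial Design section gives the number of donations: "High-frequency plasma donors (HFPDs) donating plasma 3 times every 2 weeks (in total 24 times"), against 8 for RFPDs and 2 whole-blood donations for controls. If falls are roughly proportional to level, donors who start high fall furthest in ng/mL, and the W1 spread between donors ends up in the residual of a model that contains group alone.

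What is at stake is the width of the intervals, chiefly for HFPD-RFPD and then HFPD-control. The sample is fixed and W1 is already measured, so the precision needs no new data.

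**Working it through.** **Inputs from the SAP.**
- Plasma per donation: 720 × 0.56/(0.56 + 0.06) = 650 mL, which agrees with the stated figure.
- Plasma removed over the study: HFPD 24 × 650 = 15,600 mL; RFPD 8 × 650 = 5,200 mL; controls 2 × 450 × 0.56 = 504 mL (using the same haematocrit of 44%).
- Sample: "Samples were analysed in two batches of 96 samples in 2023 and 122 samples in 2024". That is 218 samples, so at most 109 pairs, or about 36 per arm. Pairing and the split by arm are not stated.

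**Assumed, because the SAP gives no SD, correlation or expected fall.** Donor levels are lognormal with GSD 1.8. Each measurement has independent within-person log SD 0.10. The level falls by a proportion f that differs by arm.

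**Large-sample formula.** With σ² = (ln 1.8)² = 0.3455, the slope of W18 on W1 without any fall is λ = (e^0.3455 − 1)/(e^0.3555 − 1) = 0.4127/0.4269 = 0.967. In arm k the slope of change on W1 is b = −[1 − (1 − f)λ]. The residual variance, in units of Var(W1), is r = (1 − f)²(1 − λ²). With equal arms the common slope b̄ is the mean of the three. For contrast i-j:

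SE ratio = √{[r_i + r_j + (b_i − b̄)² + (b_j − b̄)²] / [r_i + r_j + b_i² + b_j²]}

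Falls of 2/10/30% (control/RFPD/HFPD) give b = −0.053, −0.130, −0.323; b̄ = −0.169; r = 0.063, 0.053, 0.032.
- HFPD-control: √(0.132/0.202) = 0.81
- HFPD-RFPD: √(0.111/0.207) = 0.73
- RFPD-control: √(0.131/0.136) = 0.98

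**Simulation under the same assumptions** (36 per arm, HC3 standard errors), reduction in empirical SE from adding W1 with one slope:

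| Falls, control/RFPD/HFPD | HFPD-control: formula, simulation | HFPD-RFPD: formula, simulation |
|---|---|---|
| 2/10/30% | 19%, 19% | 27%, 27% |
| 0/5/15% | 8%, 10% | 12%, 14% |
| 0/3/8% | 4%, 6-7% | 6%, 6-7% |

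Repeat runs move these by a point or so.

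**Power.** For 2/10/30% the HFPD contrasts already have 100% and 98% power without W1, so the gain is narrower intervals. For 0/5/15%, HFPD-RFPD rises from 68% to 77%. For 0/3/8%, power changes by 2 points or less.

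**Range.** Over 18 raw-scale scenarios (GSD 1.5, 1.8 or 2.2; log SD 0.10 or 0.15; the three sets of falls), one slope cuts the SE by 4-25% (HFPD-control), 5-34% (HFPD-RFPD) and 2-6% (RFPD-control). A second set of assumptions, with falls built from donation volume, gave reductions for the two HFPD contrasts from 1-8% (HFPD fall about 10%) to 25-51% (about 65%). RFPD-control SE ratios there ran from 0.87 to 1.02. If only HFPDs fall (0/0/30%), one common slope raises the RFPD-control SE by 5-6%.

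**Log scale.** Adding log W1 changes the SE by about 1% or less. For 0/5/15%, HFPD-RFPD power is 89% with group alone and 90% with log W1.

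**Arm-specific slopes on the raw scale.** Once the W1 mean is treated as estimated, they give no narrowing of HFPD-control for 0/3/8%. Power is then 50% against 52% unadjusted (HFPD-control) and 23% against 25% (HFPD-RFPD).

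**The case against.** The strongest reply is that nothing here is an error. A group-only analysis of change in a randomised trial is valid: simulated type I error was 3.5-5.4% with or without W1. The allowance for similar methods also means that W1 is not excluded. This stands, and it limits the point to an inexpensive improvement. It does not remove the point, because the SAP itself lists the model inputs and none of its optional clauses adds W1.

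A second reply is that the raw scale costs more than the missing covariate. Under proportional falls that is right: log change on group alone has more power than raw change with W1 (89% against 77% for HFPD-RFPD at 0/5/15%). The two models estimate different quantities, so only power is comparable.

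A third reply is that the size is assumed, and that skewed data may send the analysis to quantile regression, which was not simulated. That also stands.

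A reader might infer that the planned contrast is biased, that chance baseline imbalance invalidates it, or that W1 would sharpen every comparison. The SAP supports none of these. Randomisation protects the unadjusted contrast, and RFPD-control has no dependable gain.

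**Conclusion.** The point holds as a precision point of low severity. Study group is the only listed independent variable, and the measured W1 level is left out of the model. On the planned raw scale, one W1 slope narrows HFPD-RFPD and HFPD-control if falls are roughly proportional to level. Under the assumed values the gain runs from about 6-7% of the SE when falls are small to about 19% (HFPD-control) and 27% (HFPD-RFPD) when the HFPD fall is 30%. The direction follows from fixed-volume removal and the donation counts. The size rests on assumed spread, within-person variation and falls, none of which the SAP supplies.

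**What to change.** Under Independent Variables, add: *W1 concentration of the same PFAS, on the same scale as the outcome*. Under Statistical Analysis, state the primary model as change (or W18) on group plus W1, with robust standard errors.

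The preferred form is log change on group plus log W1, reported as a ratio, because falls are likely to be proportional and levels skewed. The estimand is then a ratio and no longer a difference in ng/mL. Logs need positive values: LOD/2 substitution secures this for values below the LOD, but branched isomers obtained by subtraction can be zero and would need a rule.

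If the raw scale is kept, one common slope is enough for the primary model. Arm-specific slopes are at most a sensitivity analysis.

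The cost is a few lines of text and one degree of freedom. With one raw-scale slope and very skewed levels (GSD 2.2, falls 2/10/30%):
- the HFPD-control estimate shrinks slightly, from about −0.383 to −0.374;
- RFPD-control power falls from about 43% to 38-40%;
- coverage of the HFPD-control interval is 91.8%, against 93.4% unadjusted (at GSD 1.8, 94.6% against 95.1%).

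The Timeline places completion of the data set in August 2025 and the analysis in September 2025. If analysis has begun, the change needs a dated amendment.
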